#### **Risks and Benefits**

The risks of the ASCENT pilot study are minimal as participants are being potentially offered additional support and expertise to manage cancer-related pain. Nothing in this trial will impede patients them from getting whatever pain modalities they and their team agree they need. The benefits to patients include the potential for safer and more guideline-concordant pain management and lower risk of opioid exposure and dependency.

#### **Protection of Human Subjects**

Care will be taken to ensure that patients' data are protected. Data from chart review, patient-reported preferences, and patient-reported outcomes will be stored securely on password protected Mayo Clinic research servers. Clinicians will still be able to make professional judgments about the appropriateness of engaging patients in specific conversations about pain management throughout their post-surgical recovery, and may disregard EHR-prompts as appropriate.

#### **Subject Information**

Target accrual is the proposed total number of subjects to be included in this study at Mayo Clinic. A "Subject" may include medical records, images, or specimens generated at Mayo Clinic and/or received from external sources.

Target accrual: 140 (maximum). Accrual will depend on the nature and extent of sociocultural and linguistic tailoring, and the number of iterative design cycles. This total includes 40 participants for the pilot study itself, up to 40 participant interviews, up to 15 study team interviews and up to 45 providers for focus groups.

Subject population (children, adults, groups): Adults

#### Inclusion Criteria:

- A qualifying liquid or solid cancer diagnosis with visits at a participating Mayo site
- Age 18+
- NRS pain score of a 5+ out of 10
- Pain that developed (onset) or significantly worsened since cancer diagnosis
- Malignant Hematology including:
  - o Lymphoma
  - o Myeloma
  - o Chronic Leukemias

#### Exclusion Criteria:

- PHO8 score of 14 or more.
- Life expectancy less than 12 months
- Hospice enrollment
- Admitted to hospital from Long Term Care/SNF

Check all that apply (data includes medical records, images, specimens).

- Acute Leukemias
- Primary brain tumors
- Confinement to a bed or a chair more than a third of waking hours because of health complications.

## Review of medical records, images, specimens

Only data that exists before the IRB submission date will be collected.
Date Range for Specimens and/or Review of Medical Records: Examples: 01/01/1999 through 12/31/2015, or all records through mm/dd/yyyy.
Note: The Date Range must include the period for collection of baseline data, as well as follow-up data, if applicable.
The study involves data that exist at the time of IRB submission and data that will be generated after IRB submission. Include this activity in the Methods section.
Examples  The study plans to conduct a retreamentive short review and selve whice to be complete a question pairs.

 
The study plans to conduct a retrospective chart review and ask subjects to complete a questionnaire.
 

The study plans to include subjects previously diagnosed with a specific disease and add newly diagnosed subjects in the future.

The study will use data that have been collected under another IRB protocol. Include in the Methods section and enter the IRB number from which the research material will be obtained. When appropriate, note when subjects have provided consent for future use of their data and/or specimens as described in this protocol.

Enter one IRB number per line, add more lines as needed

Data Specimens Data & Specimens

Data Analysis

Power analyses may not be appropriate if this is a feasibility or pilot study, but end-point analysis plans are always appropriate even if only exploratory. Provide all information requested below, or provide justification if not including all of the information.

#### Endpoints:

#### Optimized components and process

Our target endpoint is optimization of key study processes and intervention components. We will use modified, multi-stakeholder Delphi processes to determine when a study process/component has been optimized. A process/component will be considered optimized when 80% of Delphi process participants agree that sociocultural appropriatness, usability, patient-centricity, and acceptability have been optimized. After that point no further iterative refinement cycles will occur.

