## **Research Question and Aims**

#### **Hypothesis**

This study will adapt intervention components that were previously validated in several pragmatic clinical trials: E2C2 (#18-007779), NOHARM (#20-004839) and COPE (#11-008151), for remote delivery to rural dwelling and Hispanic Cancer Survivors. We will refine the sociocultural, linguistic, IT, and clinical aspects of the intervention through iterative design cycles. We recognize that the needs of the targeted subgroups are heterogeneous and may require patient-specific matching of language, IT modes, extent of portal-based delivery, among other aspects, in order to optimize patient engagement and experience. Intervention components will be integrated and tested in a future parallel group, two-arm randomized clinical trial at six Mayo Clinic sites. The full trial is anticipated to begin later this year under a separate IRB application.

We hypothesize that an iteratively refined, EHR-based modular approach that combines specific intervention components in accordance with a patient's sociocultural, IT, and linguistic needs, will demonstrate fidelity, usability, and acceptability among our target population of Hispanic, rural dwelling, and rural dwelling Hispanic cancer survivors experiences moderate or worse pain.

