## **Part 1 – Testing the ASCENT Intervention Components**

#### Intervention

Potentially eligible participants will be identified using data found in the Epic EHR Chronicles database, including qualifying appointments, ethnicity, RUCA highly rural zip code, and cancer diagnoses (Approved in IRB# 22-008103). Patients who meet the electronic criteria listed in this protocol will receive information about our study and a pain Numeric Rating Scale (NRS) questionnaire via the patient portal, Welcome tablet functionality, or Interactive Voice Response (IVR). We are seeking a waiver of consent due to the volume of patients this would involve across the 6 participating sites, and the fact that symptom monitoring is considered a best practice in caring for cancer survivors. IVR is an automated telephone service provided by an external vendor (RevSpring). Research coordinators will attempt to enroll and formally consent patients who endorse

pain  $\geq$ 5/10 and who respond to this initial outreach. Recruitment calls will also be made to screen patients who do not respond for pilot eligibility (See Recruitment & Consent section for more details). Patients will be able to opt out of hearing more information or being contacted by a study coordinator at multiple points in the trial recruitment and enrollment procedures. After consent, participants may be sent additional education materials in an initial mailing. The engagement, intake, visit 2, final visit, and follow up calls will be recorded for fidelity monitoring. All study visits will be conducted via telephone or video call.

We will test prototype recruitment scripts in English and Spanish. At the end of the recruitment process, participants will be queried about their experience. For each call, CRCs will indicate sections of the script that seemed wordy, awkward, confusing, or prompted questions from prospecive participants. We will additionally record recruitment conversations. Tapes will be reviewed by Hispanic and rural dwelling citizen scientist ASCENT team members, ASCENT implementation scientists, and CRCs.

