## **Intervention Fidelity**

All of the above components of the intervention are regarded as "important" but not "essential" to the patient experience in the trial. We will assess fidelity by establishing check lists of essential elements for each touchpoint along the intervention trajectory including: recruitment, intake call, unscheduled CHW contacts, planning call, and scheduled PCM check-ins. For pilot activities all contacts will be recorded. Two individuals to review transcripts of the touchpoints and document whether >95% of essential elements are present. If an encounter includes fewer that 95% of the elements, the interventionalists will review training materials and role play the touchpoint with senior ASCENT team members.

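### The rule that ends refinement has no fidelity criterion, although fidelity is one of the three properties the pilot hypothesises

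*Combined protocol and SAP*

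**What the plan says.** The Hypothesis section states that the modular approach "will demonstrate fidelity, usability, and acceptability among our target population".

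The stopping rule is in the Endpoints part of the plan, under Optimized components and process. A component counts as optimized, and its refinement is over, once 80% of Delphi participants "agree that sociocultural appropriatness, usability, patient-centricity, and acceptability have been optimized. After that point no further iterative refinement cycles will occur".

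The Intervention Fidelity section sets a standard for each encounter. Two people read the transcripts and "document whether >95% of essential elements are present". The stated response to a shortfall is: "If an encounter includes fewer that 95% of the elements, the interventionalists will review training materials and role play the touchpoint". The section promises checklists for each touchpoint and then names "recruitment, intake call, unscheduled CHW contacts, planning call, and scheduled PCM check-ins". The Intervention section says "The engagement, intake, visit 2, final visit, and follow up calls will be recorded for fidelity monitoring".

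The Measurement section, under Refinement of Intervention Components, includes the fidelity checklists among the data used to judge the usability and acceptability of components. It sits them beside stakeholder review of recordings and script sections that staff found ineffective. It gives them no threshold, no method of aggregation and no decision rule.

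**The concern.** Poor delivery at a touchpoint can have two causes: the staff need more practice, or the script or guide cannot be delivered in full as written. The refinement cycles exist to find and repair the second. The stated response to low fidelity addresses the first, and the rule that closes the cycles does not ask about delivery.

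A panel could reasonably find a component culturally appropriate, usable, patient-centred and acceptable while recorded encounters keep falling below the fidelity standard. Nothing in the plan would then oblige anyone to weigh the shortfall before closing the component and carrying it into the six-site randomized trial. A delivery problem that the pilot had already recorded could weaken the intervention as delivered there. The fidelity part of the pilot's own hypothesis would also have no reported result against which to judge it.

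**Working it through.** The 80% and 95% figures are chosen cut-offs, so there is no plan figure to reproduce. The check is a comparison of sections.

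**Step 1. Hypothesised properties against stopping criteria.**

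| Property | Hypothesis | Stopping rule |
|---|---|---|
| Fidelity | yes | no |
| Usability | yes | yes |
| Acceptability | yes | yes |
| Sociocultural appropriateness | no | yes |
| Patient-centricity | no | yes |

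Two of the three hypothesised properties carry over and two others are added. Fidelity is the only one dropped.

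**Step 2. Every use of fidelity of delivery.**

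- Hypothesis: a property to be shown.
- Intervention: calls are recorded to monitor it.
- Intervention Fidelity: a standard per encounter, with retraining as the one stated action.
- Measurement: checklists are an input to refinement, with no rule attached.
- Endpoints (Optimized components and process, Response rates, Qualitative data, Future trial endpoints): no fidelity result.

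Two passages could be mistaken for filling the gap. Response rates keeps design cycles going, but in pursuit of response above 90%, not of fidelity. PROM collection uses the word fidelity, but for the capture of outcome data, not for delivery of the intervention.

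**Step 3. Does any section make fidelity a condition of closing a component?** None does. A component with many encounters below 95% can satisfy the 80% rule as written.

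**Step 4. Why a rule that every encounter must pass would be a poor remedy.** With n essential elements and one omission, the share present is (n − 1)/n. The number of elements is not stated, so n is an assumption here:

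- n = 10: 9/10 = 90.0%, below the standard
- n = 19: 18/19 = 94.7%, below the standard
- n = 20: 19/20 = 95.0%, neither above 95% nor below it
- n = 21: 20/21 = 95.2%, meets the standard

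For any checklist shorter than 20 elements, one omission fails the encounter. Requiring every encounter to pass could keep a component open indefinitely. It is better for the panel to judge a reported proportion.

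**The case against.** The strongest reply is that fidelity does reach refinement. The Measurement section lists the checklists among the refinement data, so poor delivery can inform the panel's view of usability. An unworkably long guide is itself a usability fault. It may also surface through script sections flagged by coordinators and pain care managers, or through staff ratings of how patients engaged with the Conversation Guide. This stands, and it limits the point. A reader might infer that low fidelity can lead only to retraining, or that it has no bearing on when refinement ends. The documents do not support that. What they leave out is any binding role: no threshold, no summary and no requirement that the panel see the results.

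A reader might also infer that the engagement call and final visit escape fidelity review, because the checklist section names neither. That does not follow. The section covers each touchpoint and introduces its list with an inclusive word, all pilot contacts are recorded, and the check-ins by the pain care manager could include the final visit. This is an ambiguity of naming, not a demonstrated gap in coverage.

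Finally, it would be too much to say that fidelity cannot be assessed. Recordings, two reviewers and a numerical standard will supply the data. What is missing is the pilot-level summary and its place in the decision.

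**Conclusion.** The point holds as a gap in the decision rule. Fidelity is hypothesised, absent from the criteria that end refinement, and absent from the endpoints. Retraining is the only action stated for a shortfall. The checklists are collected for refinement but have no stated role in the Delphi decision. By the letter of the plan, a component with persistently low fidelity can be declared optimized.

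The size is structural: one of three hypothesised properties. The documents give no basis for estimating how often low fidelity will occur or how far the panel would notice it unprompted, and the conclusion does not depend on either. It assumes only that the four attributes listed in the stopping rule are the complete set put to the panel. This is a cheap improvement to a minimal-risk refinement pilot, not a flaw that undermines it.

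**What to change.** 1. In Optimized components and process, add fidelity to the attributes on which 80% of Delphi participants must agree. Before the vote on a touchpoint, give the panel the proportion of encounters with its current version that met the Intervention Fidelity standard at first review, before any retraining. If a script is revised because of a shortfall, hold the vote until encounters with the revised version have been reviewed. Otherwise the new version could be closed without a fidelity check.

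2. List as a descriptive endpoint the proportion of encounters meeting the standard at first review, by touchpoint.

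As a minor clarification, confirm in Intervention Fidelity that the checklists cover the engagement call and the final visit.

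The recordings, the two reviewers and the standard are already planned, so the added work is a little tabulation. A poorly delivered touchpoint may need an extra refinement cycle. That would draw on the 40 pilot participants, since Subject Information makes accrual depend on the number of design cycles.

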#### Recruitment & Consent

Using existing Patient Reported Outcome Measure (PROM) tools, potentially eligible participants with a scheduled encounter in Medical Oncology, Hematology, or Community Medicine will be identified via an EHR report, which the study coordinator(s) will regularly pull. Those with a patient portal will be sent a study invitation via portal message prior to their encounter. Nonresponders will receive the invitation during clinical registration on an Epic Welcome tablet. Patients who do not interact with the invitation via their protal of Welcome tablet will be sent the invitation by mail. Any follow-up recruitment attempts being will be conducted via portal message, telephone, or mail. Patients who do not have a portal set up will be initially invited to participate via Epic Welcome tablet. Non responders will be approached via mail or telephone, with follow-up recruitment attempts being done via telephone. Potential participants will not be contacted more than 3 times total.

We are seeking a waiver of signed informed consent as well as a waiver of signed HIPAA for this pilot protocol consonant with our intended approach to the eventual trial. Due to the minimal risk this study poses, as well as the complexities of recruiting rural and Hispanic populations and the likelihood of including undocumented Hispanic participants, we think a waiver is justified consistent with the intent of existing regulations.

Consenting will be conducted orally, at which point the participants will be screened for inclusion and exclusion criteria. The research coordinator will administer a few IT related questions to assess technology usage and fluency.

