#### Measurement

## Refinement of Intervention Components:

Assessment of the usability and acceptability of specific intervention components and study processes will require data collection appropriate to these study components and will be tailored to each touchpoint. In addition to multi-stakeholder review of recorded interactions, CRC- and PCM-identified ineffective script sections, participant-reported experience, extent and nature of family/lay caregiver involvement, and fidelity checklists, touchpoint specific assessments will include:

Recruitment – proportion of opened and completed Epic questionnaires, proportion of patients calling the ASCENT 1-800 line to express interest.

Engagement and Intake Visits – proportion of patients who provide complete pain and SDOH histories, select a Tier 1 pain management option, and develop a SMART goal; proportion of patients requesting review of Tier 2 options, patient engagement with sections of the ASCENT Conversation Guide (assessed by PCMs and CHWs using 11-point numerical rating scales (NRS).

Planning Visit – proportion of patients requesting revisions to the recommended plan, proportion of patients completing SMART goal; category of pain intervention selected as initial focus of multi-modal pain care plan; type of participant-selected provider as PCM contact.

Final Visit – proportion of patients able to receive and initiate use of modality selected during the planning visit, category of barriers impeding receipt of recommended pain care, general assessment of ASCENT program (NRS).

Follow Up Visits & NRS pain surveys: Proportion of patients completing surveys by administration mode, cause of pain escalation (categorical), participant-perceived barriers (categorical).

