#### Response rates

Our goal is to achieve >90% response rates for PROM assessments, recruitment questionnaires, and remote pain assessments. Iterative design cycles will continue with different modes, delivery approaches, follow up for non-response, and preface text.

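### Do the 80% Delphi stop and the >90% response goal give conflicting rules for ending the refinement cycles?

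*Combined protocol and SAP*

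**What the plan says.** Under Endpoints, the subsection on optimized components and process makes optimization the target endpoint and covers both study processes and intervention components. Its criterion is a vote: "A process/component will be considered optimized when 80% of Delphi process participants agree" on four attributes (sociocultural appropriateness, usability, patient-centricity and acceptability). The consequence follows at once: "After that point no further iterative refinement cycles will occur".

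The next subsection, Response rates, reads: "Our goal is to achieve >90% response rates for PROM assessments, recruitment questionnaires, and remote pain assessments". Its only other sentence is: "Iterative design cycles will continue with different modes, delivery approaches, follow up for non-response, and preface text". It does not mention the Delphi vote, a limit on cycles or a denominator.

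Three other places bear on the point:
- Refinement of Intervention Components, under Measurement, says: "Assessment of the usability and acceptability of specific intervention components and study processes will require data collection". The assessments listed there include completion of the Epic questionnaires and completion of surveys by mode.
- PROM collection asks for baseline PROMs after consent and before engagement, assesses the proportion responding to each patient's preferred mode, and pursues non-responders through other modes and finally by telephone.
- Subject Information says of the accrual ceiling: "This total includes 40 participants for the pilot study itself". It also says: "Accrual will depend on the nature and extent of sociocultural and linguistic tailoring, and the number of iterative design cycles".

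**The concern.** PROMs, recruitment questionnaires and remote pain assessments fall under both subsections. Suppose the Delphi panel reaches 80% on one of them while observed response is 90% or lower. The first subsection closes refinement. The second, read as a condition, keeps it open. No sentence ranks the two, and response rate is not among the four attributes put to the vote. A process could then be reported as optimized while it misses the pilot's own response goal.

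Two features add to the worry. Accrual is tied to the number of cycles, and that number is not fixed. The denominator for the response goal is also unstated. Because baseline PROMs are needed before engagement, response counted only among those who proceed would be complete by design. Optimization and completeness of data collection are main outputs of this pilot, so an ambiguity here deserves a check.

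**Working it through.** No sample size, power or error rate is at issue, and the plan gives no figure to reproduce. The check is a comparison of the two subsections, followed by arithmetic on what the response goal means with 40 people.

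**1. The two statements side by side.**
- The Delphi subsection has a criterion (80% agreement), a consequence (cycles end) and no exception.
- The response subsection has a goal (above 90%) and a list of things to vary: modes, delivery, follow-up and preface text. It does not say that cycles run until the goal is met, that response is a condition for optimization, or that cycles go on after Delphi agreement.

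A second stopping condition has to be inferred from the two sentences standing together. The difference between refinement cycles and design cycles does not help, because the Hypothesis section describes refinement as taking place through design cycles. The plain reading is that the vote decides when cycles end, and the response goal says what they aim for and what may be changed.

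**2. Can response data reach the vote?** Yes. The Measurement section places questionnaire and survey completion within the assessment of usability and acceptability, which are two of the four attributes voted on. No threshold is attached, but the panel has a route to the data.

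**3. Are the cycles bounded?** Subject Information allows 40 pilot participants, which limits PROM and pain-survey cycles. Recruitment questionnaires go out before consent, so the 40 does not limit them directly, but they end in practice when pilot recruitment ends.

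**4. What above 90% means.** With n = 40, the smallest qualifying count is floor(0.9 × 40) + 1 = 37, and 37/40 = 92.5%. A count of 36/40 is exactly 90.0% and misses. The exact binomial chance of at least 37 of 40, with the true response rate assumed, is:

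| Assumed true response | Chance of observing >90%, n = 40 |
|---|---|
| 80% | 2.8% |
| 85% | 13.0% |
| 90% | 42.3% |
| 95% | 86.2% |

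Missing the goal is therefore a realistic outcome, and the case described in the concern could occur.

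**5. What a response condition on each version would do.** If closure required the current version's observed response to exceed 90%, the 40 participants would be divided among versions. Assume 10 per version. Since 9/10 is exactly 90%, the condition needs 10/10. At a true response of 95%, the chance is 0.95^10 = 0.599, so a version that truly exceeds the goal fails with chance 1 − 0.599 = 0.401. With 20 per version, 19/20 is needed, the chance at 95% is 73.6%, and the failure chance is 26.4%.

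**6. Denominators.** Take assumed counts: 40 consent, 34 complete baseline PROMs and proceed, and 32 of those complete exit PROMs.
- Baseline: 34/40 = 85%, or 34/34 = 100%. The second figure removes the very non-responders whom the PROM collection section sets out to pursue, so the plan already implies that those asked are the denominator.
- Exit: 32/40 = 80%, or 32/34 = 94.1%. Here the plan is silent, and the choice could move the result across 90%.

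**The case for a change.** The strongest reply is that the response subsection says cycles will go on, which is directive, and that nothing declares the Delphi rule to be in charge. A team that took the sentence at face value could run another cycle on data for which the Delphi rule says stop. Optimization is the target endpoint, so how it is reached should be settled before response data are seen, and a sentence or two would settle it.

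Part of this stands. The subsections do not refer to each other, and the exit-PROM denominator is left open. It does not follow that the plan gives two stop rules, because only one is written as a rule. A process that the panel judges optimized and that has, say, 85% response is not self-contradictory. Those are two results under two endpoint headings, and both can be reported.

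Recruitment questionnaires may look the likeliest to miss the goal, given the contact limit: "Potential participants will not be contacted more than 3 times total". The documents do not establish this. The portal, tablet and mail steps in Recruitment & Consent concern the study invitation. Part 1 sends the pain questionnaire by portal, tablet or automated call, with recruitment calls to non-responders. How these count toward three contacts is not stated, and no expected response rate is given.

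**Conclusion.** The concern does not call for a change. Followed as written, the pilot stops refining a process on Delphi agreement and reports observed response beside the >90% goal, which is a sound result for a single-group pilot that does not use its PROM data to estimate effectiveness. A sentence saying which subsection governs would record the natural reading and alter no calculation.

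The stronger alternative, making closure depend on each version's observed response, is a debatable trade-off. A version truly at 95% would miss about 40% of the time with 10 people per version and about 26% with 20. Both group sizes and the 95% are assumptions, since the plan does not say how many people will see each version.

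The unstated exit denominator is a gap that analysts fill sensibly by giving the counts: those consented, those who proceeded and those who completed. The conclusion rests on reading the response figure as the goal the plan calls it. It would need another look if the sponsor intended that figure as a binding condition.
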